## 3.1.2 Study Treatment Phase (start of the study intervention)

There will be a 14-day period prior to the start of the study intervention during which time all subjects will maintain a standard diet/PERT dose. Subjects who were taking PPIs or H2 medication at the time of the screening/consent visit, will discontinue these medications for the duration of the study. This 14-day period prior to the start of the intervention will also serve as a washout period from these medications for these subjects. After this 14-day period, treatment with omeprazole or placebo will commence. After completing 28 days of treatment with omeprazole or placebo, subjects will have a second study visit, during which the first set of assessments will be completed. All study visits will occur at outpatient research offices of the Center for Human Phenomic Science (CHPS) at The Children's Hospital of Philadelphia (CHOP), a pediatric health care center. Eligible subjects will be enrolled into the study and come to CHOP for the study visits. Refer to Table 1 for list of assessments and the study timeline for the pace of recruitment.

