## 3.1.3 Second Treatment Phase

After completing the second study visit, there will be a 14-day washout period during which subjects will discontinue their study medication but continue their standard diet/PERT use. Subjects will then cross over to the other treatment arm and undergo an additional 28 days of treatment with omeprazole or placebo. At the end of this treatment period, they will have a third study visit that will include the outcome measure assessments.

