## 4 STUDY PROCEDURES

## 4.1 Consent Visit (Visit 1)

- Review of health history including prior and concomitant medications
- Review demographics
- Informed Consent
- Review of diet pattern
- Subjects asked to maintain a moderate to high fat diet throughout the study
- Subjects asked to maintain their clinically established PERT dose throughout the study
- Subjects asked to wean PPI or H2-receptor antagonist medication, if taking
- Simple anthropometrics
- Stool collection if needed
- Sexual maturity self-assessment (age <18y, n=12)

- GI symptom questionnaire
- Urine pregnancy test (female subjects)
- Distribute arm 1 study medication

Protocol	Day 1	Da	ys 2-15			Day	/s 16-43					
Visit 1: Consent and Randomization	- Clarify diet & PERT - Questionnaires - Elastase (if needed)			l-day washout p RA medication, i Istain on standar h fat diet onfirm standardi	f applicable rd moderate	to	- Randomized treatment to either omeprazole (PPI) or placebo for 28 days					
	Day 44	Day 45		Day 46	Day 47	Day	48	Day 49	Day 50	Days 51-		
Visit 2: After 28-day treatment with PPI or placebo	- Fast from 8pm - No dairy - Remain on standard PERT	- MBT - 7am-4p - Serum la - Anthros  If ≥18 yea - SmartPil - Fast fror 12am	bs a rs: ll	- Resume moderate- high fat diet If ≥18 years: - SmartPill at 8am - 6hr fast	- Diet record (day 1)	- Die reco (day - 72 Stoo (day	ord v 2) -hr ol	- Diet record (day 3) - 72-hr Stool (day 2)	-72-hr Stool (day 3)	- 14-day washout period from treatment placebo		

	Days 65-92	2 – Randomized	crossover treatn	nent (PPI to p	lacebo, or pla	acebo to PPI)	for 28 days	
	Day 93	Day 94	Day 95	Day 96	Day 97	Day 98	Day 99	Day 100
Visit 3:  After 28-day crossover treatment with placebo or PPI	- Fast from 8pm - No dairy - Remain on standard PEM	-MBT - 7am-4pm -Serum labs - Anthros  If ≥18 years: - SmartPill - Fast from 12am	- Resume moderate- high fat diet If ≥18 years: - SmartPill at 8am - 6hr fast	- Diet record (day 1)	-Diet record (day 2) - 72-hr Stool (day 1)	-Diet record (day 3) - 72-hr Stool (day 2)	-72-hr Stool (day 3)	- Return to usual care and medication regimen - Return to usual diet

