## 4.2 Study Treatment Phase

After the screening and consent visit, subjects will have two visits in this study. Visit 2 will be after 28 days of either omeprazole or placebo. After a 14-day washout period from study intervention of either treatment or placebo, subjects will cross over to the opposite treatment and receive the alternate therapy for 28 days. Visit 3 will take place at the completion of this 28-day period of either treatment or placebo. Assessments at both Visit 2 and 3 are identical.

#### 4.2.1 Visit 2

Visit 2 takes place over seven total days, detailed below:

#### Day 1

- Regular lunch/dinner except for no intake of dairy products
- No alcohol intake
- Normal daily activity
- Fast overnight starting at 8pm

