## Day 3 - SmartPill® Cohort returns to CHOP CHPS/NGL

- All subjects maintain events diary, continue moderate fat diet
- SmartPill® cohort:
  - Takes SmartBar® study breakfast, followed by SmartPill®
  - Fasts for six hours during study

## Day 4

- Moderate fat diet
- 3-day weighed food record begins
- Food record Day 1
- Maintain adverse events diary
- SmartPill® cohort monitors for passage of capsule and returns monitoring belt upon completion of the study

#### Day 5

- Moderate fat diet
- Food record Day 2
- Stool collection begins (72-hour fecal fat), store frozen until brought to CHOP
- 72-hour stool Day 1
- Maintain adverse events diary
- SmartPill® cohort monitors for passage of capsule and returns monitoring belt upon completion of the study

#### Day 6

- Moderate fat diet
- Food record Day 3
- 72-hour stool Day 2
- Maintain adverse events diary

## Day 7

- Moderate fat diet
- 72-hour stool Day 3
- Maintain adverse events diary

#### 4.2.2 Visit 3

Visit 3 takes place over seven total days, detailed below:

#### Day 1

- Regular lunch/dinner except for no intake of dairy products
- No alcohol intake
- Normal daily activity
- Fast overnight starting at 8pm

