## 4.5 Subject Completion/Withdrawal

For subjects with CF and EPI who were naïve to PPI at the start of the study, at the end of participation in the study (all collections are complete for Visit 3) omeprazole will be discontinued and they will and resume their usual care without acid suppression. For subjects with CF and EPI who were receiving acid suppression with PPI or H2RA prior to the start of the study, at the end of participation in the study (all collections are complete for Visit 3), omeprazole will be discontinued and they will resume their usual care, including their acid suppression product and dose they were receiving before the study began.

Subjects may withdraw from the study at any time without prejudice to their care. They may also be discontinued from the study at the discretion of the Investigator for lack of adherence to study treatment or visit schedules, or adverse events. The Investigator or the Sponsor may also withdraw subjects who violate the study plan, or to protect the subject for reasons of safety or for administrative reasons. It will be documented whether or not each subject completes the clinical study. If the Investigator becomes aware of any serious, related adverse events after the subject completes or withdraws from the study, they will be recorded in the source documents and on the CRF.

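### The plan does not settle whether study drug is taken during the seven-day assessment visits: on one reading the primary CFA stool is collected 5 to 7 days off drug, on the other the supply is two capsules short.

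*Combined protocol and SAP*

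**What the plan says.** Some parts of the plan end dosing before the assessments:

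- The flow table in Section 4.1 lists "Randomized treatment to either omeprazole (PPI) or placebo for 28 days" against Days 16-43, and the crossover treatment against Days 65-92.
- Section 3.1.2: "After completing 28 days of treatment with omeprazole or placebo, subjects will have a second study visit".
- Section 4.2: "Visit 2 will be after 28 days of either omeprazole or placebo".
- Section 7.1.1 supplies 33 days of drug per period, described as 28 days of dosing with a 20% allowance for spares.

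Other parts carry dosing through the assessments:

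- Section 3.1.3: "After completing the second study visit, there will be a 14-day washout period during which subjects will discontinue their study medication". Section 4.2.1 makes that visit a week long: "Visit 2 takes place over seven total days, detailed below".
- The flow table enters the "14-day washout period from treatment placebo" from Day 51 and starts the second treatment on Day 65.
- Section 4.5: "at the end of participation in the study (all collections are complete for Visit 3) omeprazole will be discontinued". This is weaker support, because the paragraph is about returning to usual care at the end of participation.
- Section 5.2.1 describes the CFA comparison as one between subjects on PPI and subjects on placebo. The Study Phases entry of the synopsis has subjects resume their normal medication once the last stool collection is done.

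The CFA stool comes late in the visit. On visit Day 5 (study Day 48) the list reads "Stool collection begins (72-hour fecal fat), store frozen until brought to CHOP", and collection runs to visit Day 7 (Day 50). Visit 3 follows the same pattern on Days 97-99. Neither the visit day lists nor the flow-table cells for Days 44-50 and 93-99 tell subjects to take study drug or to stop it.

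**The concern.** CFA is the only primary endpoint, and the crossover exists to compare it on and off omeprazole. That requires the assigned treatment to be in effect while the fat is eaten and the stool collected. If dosing ends at 28 days, the whole stool collection falls in a drug-free interval. The plan itself uses 14 days off drug as its washout, and stool days 5 to 7 lie 36% to 50% of the way through such an interval (5/14 to 7/14). Any fading of effect by then shrinks the observed contrast.

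If dosing is meant to continue, the supply was not sized for it. If subjects or staff resolve the silence differently, exposure in the endpoint window will also differ between subjects.

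**Working it through.** **Inputs.** Dosing days, visit days, washout start and arm 2 start are from the Section 4.1 flow table. The seven-day visit and the stool days are from Sections 4.2.1 and 4.2.2. The dose is 20 mg a day in 20 mg capsules, so one capsule a day (Sections 7.1.1 and 7.1.3). The supply is 33 per period (Sections 7.1.1 and 7.1.4).

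**1. The plan's own figures.** Days 16-43: 43 - 16 + 1 = 28. Days 65-92: 92 - 65 + 1 = 28. Supply: 28 x 1.2 = 33.6, given as 33. The supply is therefore built on 28 dosing days.

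**2. Reading A: last dose on Day 43 and Day 92.**

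| Assessment | Period 1 | Period 2 | Days after last dose |
|---|---|---|---|
| Malabsorption blood test | Day 45 | Day 94 | 2 |
| SmartPill | Day 46 | Day 95 | 3 |
| Food record | Days 47-49 | Days 96-98 | 4-6 |
| CFA stool | Days 48-50 | Days 97-99 | 5-7 |

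The drug-free interval before arm 2 would be Days 44-64, or 64 - 44 + 1 = 21 days, against the stated 14. The extra week does no harm in itself, but it shows that the table's washout fits only dosing to Day 50 (Days 51-64: 64 - 51 + 1 = 14).

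**3. Reading B: dosing through the last stool day.** Doses needed: 50 - 16 + 1 = 35 and 99 - 65 + 1 = 35. The last days that 33 capsules cover are 16 + 33 - 1 = 48 and 65 + 33 - 1 = 97. Days 49-50 and 98-99 are uncovered, which is two of the three stool days in each period.

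**4. Capsule return.** Section 7.1.1 has unused capsules returned at Visits 2 and 3. The only clinic day that all subjects attend in Visit 2 is Day 45, the day on which arm 2 drug is handed out (Section 4.2.1). If capsules are returned then, a subject has no arm 1 drug for Days 46-50 but already holds the arm 2 bottle.

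**5. Illustration of the stakes.** Section 6.4 plans 22 subjects for a 3-point CFA increase with SD 5, using a paired t-test at alpha 0.05. I take the test as two-sided and the SD as that of the within-subject differences. The normal formula gives ((1.960 + 0.842) x 5/3)^2 = 21.8, so 22, which reproduces the plan. Exact paired-t power at 22 is 76.5%. The documents give no offset rate, so the share of effect remaining at stool collection is an assumption:

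| Share remaining | Effect (points) | Power, n = 22 |
|---|---|---|
| 100% | 3.00 | 76.5% |
| 75% | 2.25 | 52.1% |
| 50% | 1.50 | 26.9% |
| 25% | 0.75 | 10.3% |

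These rows show how sensitive power is to dilution. They do not estimate the loss.

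**The case against.** The best defence is that continued dosing is the intended reading. Wherever the plan says when study drug is discontinued, it puts the stop after the assessments (Sections 3.1.3 and 4.5). The synopsis and Section 5.2.1 agree, and nothing tells a subject to stop on Day 43 or Day 92. The 28 days can be read as the time on treatment before assessment begins. Silence in the visit day lists proves little, since those lists do not mention PERT either and PERT is required throughout.

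On that reading the shortfall is two capsules. It affects only subjects who miss fewer than two of 35 doses, and Section 7.1.4 has staff in regular contact about supply. The fat counted in CFA is also eaten a day before the stool, on Days 47-49. By that measure 34 doses are needed, only Day 49 is uncovered, and the gap on the other reading is 4 to 6 days.

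Much of this is fair. It makes continued dosing a plausible intention and narrows the supply gap. It does not remove the conflict. The dosing days and the supply are both written for 28 days, no instruction tells subjects to go on dosing, and capsules go back at a visit whose common clinic day precedes the stool collection. Leftover capsules from missed doses, or a timely telephone call, do not replace a written rule for the primary endpoint window.

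**Conclusion.** The concern holds. Following the stated dosing days puts the whole CFA stool collection 5 to 7 days off drug in both periods. Following the implied dosing to Days 50 and 99 leaves a fully adherent subject without capsules for two of the three stool days. The second figure assumes one capsule a day, none lost, and none returned before the collection ends.

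The direction of any bias is toward no difference. Its size depends on how quickly the effect of omeprazole on fat absorption fades, which the documents do not give, and on what subjects are told in practice. This should be corrected because it touches the primary endpoint and is cheap to put right. It does not show that the endpoint is in fact measured off drug.

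**What to change.** State in the flow table and in Sections 3.1.2, 3.1.3, 4.2 and 7.1.1 that the assigned treatment is taken daily through the last stool collection day: Days 16-50 and 65-99. In Sections 7.1.1 and 7.1.4, supply at least 35 capsules plus spares per period; 35 x 1.2 = 42 keeps the stated margin. Collect unused capsules after the stool collection, count adherence against 35 doses, and tell subjects not to open the arm 2 bottle before Day 65.

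**Cost.** Seven more days of 20 mg omeprazole or placebo per period, and up to 42 - 33 = 9 more capsules per subject per period, so at most 9 x 2 x 24 = 432. The stated treatment length changes from 28 to 35 days wherever it appears, and the timing of capsule return changes. There is no extra visit, and the Day 51-64 washout and Day 65 start stay as they are.

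**Alternative.** If treatment must stay at exactly 28 days, move the seven-day visit inside it. In period 1 that is Days 37-43, with stool on Days 41-43, and the 33 capsules are enough. Every assessment then falls a week earlier in treatment, so extending dosing is preferable.

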## 4.2 Study Treatment Phase

After the screening and consent visit, subjects will have two visits in this study. Visit 2 will be after 28 days of either omeprazole or placebo. After a 14-day washout period from study intervention of either treatment or placebo, subjects will cross over to the opposite treatment and receive the alternate therapy for 28 days. Visit 3 will take place at the completion of this 28-day period of either treatment or placebo. Assessments at both Visit 2 and 3 are identical.

#### 4.2.1 Visit 2

Visit 2 takes place over seven total days, detailed below:

#### Day 1

- Regular lunch/dinner except for no intake of dairy products
- No alcohol intake
- Normal daily activity
- Fast overnight starting at 8pm

## Day 2 - Visit to CHOP CHPS/NGL

- Insert blood-drawing intravenous catheter
- Baseline blood draw for MBT / study labs drawn (Vitamins A/E, Magnesium, essential fatty acids)
- Administer MBT study meal (breakfast)
- MBT hourly blood sample for 9 hours
- After hour 6, low-fat study lunch
- Anthropometry (height, weight, skinfolds, circumferences)
- Questionnaires: Health History and medications, Quality of life questionnaire (CF-QOL), PROMIS, GI symptom questionnaire, Adherence, Adverse Events

- Instructions will be given for collection and shipping for: stool collection (72-hour fecal fat analysis), 3-day weighed food records, and adverse events diary
- Provide arm 2 study medication
- SmartPill® cohort will fast overnight starting at 12:00am

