Adverse Events Diary: Subjects will be asked about all adverse events at both Visits 2 and 3, and asked to rate by intensity (mild, moderate, severe). Serious adverse events will be reported as per various policies in a timely manner to CHOP IRB, and CHPS.

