## 8.3 Definition of an Adverse Event

An adverse event is any untoward medical occurrence in a subject who has received an intervention (drug, biologic, or other intervention). The occurrence does not necessarily

have to have a causal relationship with the treatment. An AE can therefore be any unfavorable or unintended sign (including an abnormal laboratory finding, for example), symptom, or disease temporally associated with the use of a medicinal product, whether or not considered related to the medicinal product.

All AEs (including serious AEs) will be noted in the study records and on the case report form with a full description including the nature, date and time of onset, determination of non-serious versus serious, intensity (mild, moderate, severe), duration, causality, and outcome of the event.

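### The adverse-event diary is scheduled on 10 of about 100 study days, none in a labelled treatment or washout block; handing it out at Visit 1 would be a cheap improvement

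*Combined protocol and SAP*

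**What the plan says.** The diary appears in the day-by-day procedures of the two assessment visits. On Day 2 of Visit 2 (Section 4.2.1), and in the same words at Visit 3 (Section 4.2.2): "Instructions will be given for collection and shipping for: stool collection (72-hour fecal fat analysis), 3-day weighed food records, and adverse events diary". On Day 3 of each visit: "All subjects maintain events diary, continue moderate fat diet". Days 4 to 7 each carry the entry "Maintain adverse events diary". On length, "Visit 2 takes place over seven total days, detailed below", and Visit 3 is described in the same way.

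The Visit 1 list in Section 4.1 does not mention a diary. Table 1 has no diary row. Its adverse-events row carries two marks, which Section 5.1.3 places at Visits 2 and 3.

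The paragraph headed Adverse Events Diary in Section 5.1.3 describes something different, an enquiry at the visits: "Subjects will be asked about all adverse events at both Visits 2 and 3, and asked to rate by intensity (mild, moderate, severe". The adherence paragraph of the same section adds that phone calls also gather adverse-event information. Section 7.1.4 promises regular phone or text contact and gives no interval. The monitoring plan that follows the synopsis, and Sections 8.1 and 9.4.1, commit to collection or monitoring throughout the study.

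Section 8.3 requires every adverse event to be recorded "with a full description including the nature, date and time of onset", and also its duration.

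The flow table in Section 4.1 labels Days 16–43 as "Randomized treatment to either omeprazole (PPI) or placebo for 28 days", gives the crossover block as Days 65–92, and starts a "14-day washout period from treatment placebo" at Day 51.

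**The concern.** Section 5.3 monitors safety through adverse-event reporting, and Section 6.3.3 summarises events by relationship to study drug. Section 9.4.2 names the expected effects of omeprazole, such as headache, flatulence, diarrhea and nausea, and a temporary return of reflux symptoms in subjects who stop long-term acid suppression. Events of this kind can be brief and are hard to date weeks later.

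In this crossover the onset date helps decide whether an event belongs to a treatment block or to a washout. A daily record made at the time is the most direct source of that date. As the visit procedures stand, that record is called for only in the two assessment weeks, after each labelled 28-day block has ended.

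**Working it through.** This is a day count on the plan's own calendar.

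**The plan's own figure.** The flow table runs: consent 1, washout 14, treatment 28, Visit 2 7, washout 14, treatment 28, Visit 3 7. 1 + 14 + 28 + 7 + 14 + 28 + 7 = 99, plus Day 100 for return to usual care = 100. Section 3.3.1 adds up as 1 + 48 + 48 = 97. Both agree with its approximate 100 days.

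**Mapping.** Visit 2 Day 1 is study Day 44, so visit Days 3–7 are study Days 46–50. Visit 3 Day 1 is study Day 93, so visit Days 3–7 are study Days 95–99.

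| Block | Study days | Length | Diary days inside |
|---|---|---|---|
| First washout | 2–15 | 14 | 0 |
| First treatment | 16–43 | 28 | 0 |
| Visit 2 | 44–50 | 7 | 5 |
| Second washout | 51–64 | 14 | 0 |
| Second treatment | 65–92 | 28 | 0 |
| Visit 3 | 93–99 | 7 | 5 |

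Diary days: 5 + 5 = 10 (12 if Day 2 of each visit is counted). Overlap with labelled treatment: 0 of 28 + 28 = 56. Overlap with labelled washout: 0 of 14 + 14 = 28.

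**Recall span.** The dated adverse-event questions are on Day 2 of each visit, study Days 45 and 94. If no contact occurs in between, the longest look-back is 45 − 1 = 44 days at Visit 2 and 94 − 50 = 44 days at Visit 3.

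**Diary days on study drug.** This depends on which section sets the end of dosing:

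- Flow table in Section 4.1: treatment is labelled Days 16–43 and 65–92, so 0 of 10.
- Sections 3.1.3 and 4.5: the first drug stops after Visit 2 is completed, and omeprazole stops once the Visit 3 collections are complete. Dosing to Days 50 and 99 gives 10 of 10.
- Section 7.1.1: a 33-day supply. At one capsule a day it lasts to 16 + 33 − 1 = Day 48 and 65 + 33 − 1 = Day 97. That covers Days 46–48 and 95–97, so 6 of 10.

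**Where recall error can move an event.** The Day 45 question follows the first washout and first treatment block only. The Day 94 question looks back over the second washout and second treatment block, and the second treatment does not start until Day 65. A wrong date within one look-back can therefore shift an event between a washout and the treatment block next to it. In the omeprazole-first sequence, symptoms after omeprazole stops, in Days 51–64, could be placed in the placebo block at Days 65–92.

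**The case against.** The strongest reply is that the diary is only one of several sources. Subjects are asked about all adverse events at Visits 2 and 3, phone contacts gather them too, and the monitoring plan after the synopsis has the principal investigator reviewing the ongoing collection weekly. The PROMIS gastrointestinal forms cover several of the expected effects, and serum magnesium is measured in both periods. In a Phase IV study of an over-the-counter dose, asking at visits and by phone is defensible. This stands, and it makes 44 days a worst case. It does not supply an interval for the calls or an instrument for the ongoing collection, and Section 4.3 allows no unscheduled visits.

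A reader might infer more than the documents support:

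- *That the diary is issued only on Day 2 and sent back after Day 7.* No hand-out or return date is stated. The text gives instructions for collection and shipping, and Day 7 carries the last entry. Section 5.1.3 could even be read as reviewing a diary kept beforehand.
- *That the diary misses all exposure to study drug.* Under Sections 3.1.3 and 4.5 all 10 diary days are on drug. The zero applies only to the labelled blocks.
- *That events in treatment and washout go uncollected.* The other sources rule this out.
- *That events will be credited to the wrong treatment.* The visit questions bracket each period, so the ordinary error is between a treatment block and its adjacent washout. The diary schedule is the same in both periods, so its timing does not by itself bias the comparison.
- *That Section 8.3 is contradicted.* It fixes what is recorded for each event. Interviews and calls may supply the dates, though less reliably.

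**Conclusion.** The point holds as a cheap improvement; it is not an error in the plan. The visit procedures schedule the diary on 10 of about 100 days. The 56 labelled treatment days and 28 labelled washout days depend on recall and on calls of unstated frequency. Mild, transient events may be missed or misdated there, and reflux symptoms after stopping acid suppression are the clearest example. The second washout is not symmetric, because only the omeprazole-first sequence stops omeprazole before it. The documents do not allow the size or direction of any resulting bias to be stated.

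This rests on two assumptions: that the visit days map one-to-one onto the flow-table calendar, and that the diary entries in Sections 4.2.1 and 4.2.2 are complete. The 44-day span further assumes no interim contact. That Section 5.1.3 describes the diary differently from Sections 4.2.1 and 4.2.2 needs none of these assumptions.

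**What to change.** In Section 4.1 and Table 1, hand out the existing diary at Visit 1. Have subjects complete it when an event occurs, from Day 2 through the last stool day (Day 99), giving onset date, stop date and intensity. Review it on Day 2 of Visits 2 and 3 and at phone contacts, and state how often those contacts take place. Rewrite the diary paragraph in Section 5.1.3 to match Sections 4.2.1 and 4.2.2, with the start, duration and return of the diary stated.

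The cost is protocol wording and an earlier hand-out of a form already in use. The burden on subjects, some as young as 12, extends over 99 − 2 + 1 = 98 days instead of 10. Recording only when an event occurs keeps it modest, and Section 7.1.4 already gives subjects a calendar at Visit 1.

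Separately, the end of dosing in each period needs to be reconciled across Sections 3.1.3, 4.1 (flow table), 4.5 and 7.1.1, so that events in the assessment weeks can be classed as on or off study drug.
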